## 9.2 Sample Size and Randomization

Our pilot study demonstrates an increase in HF HRV after 6-week exhale=inhale slowing breathing (N=9, mean  $58 \pm SD 248$ ) or after 6-week exhale>inhale slow breathing (N=9,  $173 \pm 531$ ). The pooled SD from the two groups is 406, which is similar to published values among health adults. By 12 weeks, we expect that the difference in HF HRV between the two groups will be 265, and a sample size of 38 per arm will give us 80% power to detect this effect at a 0.05 two-sided significance level. Accounting

for 20% drop out, we will enroll 50 participants per arm. If the difference detected is 280 and 300, the power will be 84% and 89%, respectively.

With 50 participants per arm, we will have 80% power to detect a 5.2-point difference in 12-week PROMIS Anxiety Scale reduction assuming a SD of 8 and a type I error of 0.05. With a total N of 76, the study is able to detect a correlation coefficient of 0.7 between changes in HF HRV and changes in PROMIS Anxiety with a margin of error of 0.14.

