### 9.6 Data Analyses

Standard graphing and screening techniques will be used to detect outliers and to ensure data accuracy. Distributions of continuous outcomes will be assessed for normality. If normality is violated, proper data transformation will be applied or non-parametric analysis methods will be considered. Summary statistics for both continuous and categorical variables will be provided by randomization groups to describe the study sample.

This is a two-arm randomized study with repeated measures. The effects of either of the slow breathing interventions on HF HRV, PROMIS Anxiety and other endpoints will be estimated as within-subject mean change from baseline to 12 week, along with their 95% confidence intervals. A paired t-test will be performed to compare the endpoints within the group. The difference between the two treatment groups will be estimated by the mean difference in the within-subject changes, along with their 95% confidence intervals, and a t-test will be performed. If normality is violated, proper data transformation will be applied.

Mixed-effect models will also be used to analyze the data with a random subject effect and with intervention (exhale>inhale vs. exhale=inhale), time points (6 week and 12 week), baseline measurements and interaction between intervention and time points as fixed effects. Change in the outcomes from baseline to 6/12 weeks will be used as responses. We will include covariates age, gender, and baseline psychological stress in the models to adjust for their effects.

Specific inferences on effects of interest will be made by reporting a point estimate along with a 95% confidence interval and the p-value. Hypotheses will be tested at the level of  $\alpha=0.05$ .

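### The mixed model's single random subject effect assumes equal variance of change at weeks 6 and 12; if that is wrong, its week-12 interval is miscalibrated in either direction

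*Combined protocol and SAP*

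**What the plan says.** Section 9.6 describes two between-arm analyses.

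- The one listed first is a two-sample t-test: "The difference between the two treatment groups will be estimated by the mean difference in the within-subject changes". The change it refers to is defined just before as the "within-subject mean change from baseline to 12 week".
- The second is introduced with "Mixed-effect models will also be used to analyze the data with a random subject effect". Its fixed effects are intervention, time point (6 and 12 weeks), the baseline measurement and the intervention-by-time interaction, plus age, gender and baseline psychological stress. On the response, the section says: "Change in the outcomes from baseline to 6/12 weeks will be used as responses".

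No residual covariance structure, visit-specific variance or robust standard error is mentioned. Section 9.6 expects 20% of post-randomization assessments to be missing and cites the mixed model's ability to use participants who miss one visit. It asks for a point estimate, 95% confidence interval and p-value, tested at 0.05, and does not say which of the two analyses is confirmatory.

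Section 9.2 gives 6-week pilot SDs for the change in HF HRV of 248 and 531 (9 per arm). It adds: "The pooled SD from the two groups is 406, which is similar to published values among health adults". That SD is used for the 12-week calculation. For PROMIS Anxiety it gives a single SD of 8.

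**The concern.** Each participant contributes two responses. A random subject intercept with homogeneous residuals gives compound symmetry: one variance for both visits and one covariance between them. The interaction term lets the arm difference vary by visit, but both visit-specific differences then have standard errors built from the same averaged variance.

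The week-12 contrast is the trial's main question for HF HRV and for PROMIS Anxiety. If change is more variable at week 12 than at week 6, the model's week-12 interval is too narrow and its p-value too small. If change is less variable at week 12, the interval is too wide and power is lost. Equal variance is not assured by the design. Under Section 5.1 the first two weeks are common to both arms, so week 6 follows about four weeks of assigned breathing and week 12 about ten.

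**Working it through.** **1. The plan's own figure.** The inputs, from Section 9.2, are a difference of 265, SD 406, 38 per arm and a two-sided 0.05 level. The noncentrality is 265 / (406 × √(2/38)) = 265 / 93.1 = 2.85 on 74 degrees of freedom, which gives 80.2% power for a two-sample t-test. Differences of 280 and 300 give 84.3% and 88.9%. These match the stated 80%, 84% and 89%. The SD that gives exactly 80% is 407, so the plan assumes the same SD at week 12 as in its 6-week pilot. (Equal-n pooling of 248 and 531 gives √((248² + 531²)/2) = 414 rather than 406; this has no bearing on the ratio used below.)

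**2. The formula.** Let SD6 and SD12 be the SDs of change at each visit after the fixed effects, and let k = SD12/SD6. In balanced data the random-intercept model estimates one variance, (SD6² + SD12²)/2, where the week-12 contrast needs SD12². The sample size cancels, so

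R = model SE / true SE at week 12 = √((1 + k²) / (2k²)),

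and the type I error is 2 × (1 − Φ(1.96 × R)).

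Example for k = 1.5: R = √(3.25/4.5) = 0.850; 1.96 × 0.850 = 1.666; type I error 9.6%.

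**3. Results over a range of k.** The documents do not give k, so it is an assumption.

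| k | R | Week-12 type I error | Coverage of the 95% interval |
|---|---|---|---|
| 0.75 | 1.179 | 2.1% | 97.9% |
| 1 | 1.000 | 5.0% | 95.0% |
| 1.1 | 0.956 | 6.1% | 93.9% |
| 1.25 | 0.906 | 7.6% | 92.4% |
| 1.5 | 0.850 | 9.6% | 90.4% |
| 2 | 0.791 | 12.1% | 87.9% |

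**4. Simulation checks.** The visit correlations are assumed.

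- With 40 per arm, correlation 0.6 and 20,000 trials per ratio, common variance gave 2.3%, 5.4%, 8.0%, 10.1% and 12.5% for k = 0.75, 1, 1.25, 1.5 and 2. Visit-specific variances gave 4.9% to 5.1% throughout.
- REML fits with 50 per arm, 20% missing at each visit, correlation 0.5 and 2,000 trials per scenario gave 5.7%, 6.9%, 9.8% and 12.4% for k = 1, 1.25, 1.5 and 2, and 2.5% for k = 0.8. At k = 1.5 the error was 9.7% with no missing data and 10.2% with correlation 0.7. The t-test on 12-week change stayed between 4.3% and 5.8% in all of these runs.

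**5. Where the assumption acts.** The t-test uses only week-12 data, so k does not affect it. Without imputation, though, it omits anyone seen only at week 6, whom Section 9.3 counts in the intention-to-treat population. The mixed model keeps those participants and carries the covariate adjustment. If the multiple-imputation analysis refits the mixed model, Rubin's rules will combine variances that rest on the same assumption.

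**The case against.** The strongest reply has three parts.

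- **The first-listed analysis is sound.** The t-test on 12-week change is valid at any k, and the sample size in Section 9.2 matches it. This stands and limits the reach of the point: it matters only where the mixed model's week-12 contrast is used for inference. The plan does not exclude that use.
- **The covariance is unspecified rather than wrong.** A random subject effect can be combined with visit-specific residual variances. This also stands, but the text does not ask for that, and ordinary residuals are the natural reading.
- **Transformation may help.** Section 9.6 allows transformation when normality fails. That might also even out the variances, but the trigger is non-normality, not unequal variance.

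Two stronger readings are tempting. First, a reader might infer that the plan's own numbers point to growing variability, because the arm difference is expected to rise from 173 − 58 = 115 in the 6-week pilot to 265, and the pilot arm with the larger mean change had the larger SD. The documents do not support this. Both SDs are 6-week values from different arms with 9 participants each. What grows is a mean difference, and the calculation reuses 406, so the plan's figures correspond to k = 1 and a 5% error rate.

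Second, a reader might infer from 248 and 531 that the covariance must be estimated separately by arm. With equal arms and that SD ratio (531/248 = 2.14), the simulated mixed-model error was 4.7%. Inflation would need fewer completers in the more variable arm, and the plan gives 1:1 allocation and no dropout figure by arm.

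**Conclusion.** The point holds as a gap in specification with a real but conditional cost. As written, and with ordinary residuals, the mixed model is calibrated at week 12 only if the variance of change is the same at both visits. For SD ratios between 0.75 and 2, its nominal 5% error would lie between about 2.1% and 12.1%. The closed form assumes balanced data; simulation with 20% missing data gave similar values. The ratio is unknown, so neither the direction nor the size of any error can be read from the documents, and no inflation is shown at the plan's own SD. The t-test result is not in question. The change is still worth making, because the mixed model is the adjusted analysis and the one relied on for participants who miss a visit, and nothing in the plan makes it subordinate to the t-test.

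**What to change.** In Section 9.6, replace the random subject effect with an unstructured 2x2 within-person covariance for the week-6 and week-12 changes, fitted by REML with Kenward-Roger or Satterthwaite degrees of freedom. Keep all stated fixed effects: intervention, time point, intervention by time point, baseline measurement, age, gender and baseline psychological stress. The unstructured covariance should replace the random effect rather than sit alongside it, because with two visits it already covers the within-person correlation. If the mixed model is refitted to the imputed data sets, use the same specification there.

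The cost is one sentence in the SAP, one line of code and one extra covariance parameter (three instead of two). Little is lost if the variances turn out equal: with visit-specific variances the simulated error stayed at 4.9% to 5.1% at every ratio tried, including 1.

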#### **6.2.5 Completion/Final Evaluation**

- At 12 weeks
  - Autonomic tone
  - Catecholamine Profile
  - Questionnaires: PROMIS Anxiety Scale, Anxiety Sensitivity Index-3 (ASI-3), Beck Anxiety Inventory, Body Vigilance Scale, Panic Disorder Severity Scale, and Perceived Stress Scale-10, PROMIS Depression scale and PANAS-X.
  - Current Medications
  - Concomitant Interventions

Participants who discontinue the study intervention early will require no specific evaluations.

The reason for discontinuation will be documented. If research participants no longer want to participate in the research study, we will terminate them from the study. Participants terminated from the study will undergo no further monitoring or follow-up once they have stopped the study intervention.

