Based on our pilot study, we anticipate 20% missingness on post-randomization assessment. Mixed-effects models are robust in the sense that they can include subjects with missing data at one time point (6 week or 12 week) to estimate the effects of interest. We will also perform multiple imputation for missing data to corroborate our findings. Specifically, all the baseline variables and outcome variables will be included in the imputation model, and flexible additive imputation models and predictive mean matching approach will be used to impute missing values. We will use Rubin's method to combine the estimated regression coefficients and variances from the models based on ten imputed complete data sets. A Pearson correlation coefficient between changes in HF HRV and changes in PROMIS Anxiety will be calculated at each post-randomization assessment, for each intervention group or for all the participants respectively, along with 95% confidence interval. In addition, linear regression analysis of HF HRV changes on PROMIS Anxiety changes, age and gender will be conducted.

Per-protocol analysis will be also performed as a sensitivity analysis, and only participants who practice breathing at home at least 3 times a week and achieve prescribed breathing rate and ratio for at least 2 time periods after randomization will be included.

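### The planned imputation rests on the same missing-at-random assumption as the mixed model, so it cannot show that results survive if participants who stop do worse than similar participants who stayed

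*Combined protocol and SAP*

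**What the plan says.** Section 9.6 gives a t-test on within-subject changes to 12 weeks, then a mixed-effects model for the 6- and 12-week changes. It expects 20% missingness after randomization. Of the mixed model it says: "Mixed-effects models are robust in the sense that they can include subjects with missing data at one time point". It then adds: "We will also perform multiple imputation for missing data to corroborate our findings". The imputation uses flexible additive models with predictive mean matching, takes in the baseline and outcome variables, and combines ten data sets by Rubin's method. Treatment arm, stopping and adherence are not named as imputation variables. The one analysis labelled as a sensitivity analysis is per-protocol, restricted to participants who met the practice and breathing targets.

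Section 6.2.5 says: "Participants who discontinue the study intervention early will require no specific evaluations". It adds that terminated participants have no further follow-up, and section 8 ends research data collection at withdrawal. Sections 9.1 and 9.3 define the intention-to-treat population as randomized participants with a baseline and at least one post-randomization assessment.

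**The concern.** Whether an outcome is missing is tied by design to whether the participant stopped the breathing programme. Once someone stops or withdraws, later outcomes are mostly not collected. The open question is then whether stoppers' unobserved outcomes resemble those of participants with a similar observed history who stayed under assessment. A likelihood-based mixed model and standard predictive mean matching both answer yes by assumption. The documents never use the term missing at random, but it is the usual assumption of both methods as described.

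No planned analysis asks what happens if the answer is no. There is no delta adjustment, tipping-point analysis or reference-based imputation. The per-protocol analysis removes stoppers and does not ask how they fared. If the two methods agree, the plan's wording invites the reader to take that as support on the one matter neither can examine. This counts for more here because participants know their assignment (section 6.2.3) and one of the two primary outcomes, PROMIS Anxiety, is self-reported.

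**Working it through.** **Inputs from the documents.** Section 9.2 states "we expect that the difference in HF HRV between the two groups will be 265" and "The pooled SD from the two groups is 406"; for PROMIS Anxiety it plans a 5.2-point difference with SD 8. On dropout it allows "for 20% drop out, we will enroll 50 participants per arm". Section 9.6 expects 20% missing, about 10 of 50 per arm.

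**The plan's own figure.** The stated design is "a sample size of 38 per arm will give us 80% power to detect this effect at a 0.05 two-sided significance level". A noncentral t calculation with difference 265 and SD 406 gives 38 per arm (power 80.2%). At 38 per arm, power is 84.3% for a difference of 280 and 88.9% for 300, matching "If the difference detected is 280 and 300, the power will be 84% and 89%, respectively". Dropout inflation is 38 / 0.8 = 47.5, so 48, which the plan rounds up to 50. The HF HRV design reproduces, and the point does not rest on an error in it.

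**Shift in the arm difference.** Let p1 and p0 be the proportions missing in the two arms, and d1 and d0 the amounts by which missing outcomes are worse than missing at random implies. The change in the arm difference is p1 × d1 − p0 × d0. With equal p and equal d it is zero, so the departures must be allowed to differ by arm.

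*One-arm departure, all randomized, p = 0.20; d of 0.5 to 1 SD is an assumption:*
- PROMIS: 0.20 × 4 = 0.8 and 0.20 × 8 = 1.6 points, or 15% and 31% of 5.2.
- HF HRV: 0.20 × 203 = 41 and 0.20 × 406 = 81 units, or 15% and 31% of 265.

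*Stoppers in both arms lose the whole between-arm difference, 20% stopping in each:*
- PROMIS: 0.20 × 5.2 = 1.04 points.
- HF HRV: 0.20 × 265 = 53 units, leaving 212.

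*Defined population only.* Assume half of the 20% have no post-randomization visit. Five of 50 per arm are then excluded, and missingness at 12 weeks is 5/45 = 11%. The one-arm shifts become 0.44 to 0.89 points and 23 to 45 units.

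**Can both methods agree and both be off?** A 300-run simulation used 50 per arm, 20% stopping per arm (half before week 6), within-subject correlation 0.5, and loss of all benefit after stopping. Timing, correlation, the extent of loss and a 12-week comparator change of 58 (the pilot's 6-week value) are assumptions. Mean HF HRV differences at 12 weeks were:

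| Quantity | Mean difference |
|---|---|
| True, all randomized (expected 212) | 216 |
| t-test on 12-week completers | 268 |
| Mixed model | 268 |
| Imputation, arm in the model | 265 |
| Imputation, arm left out | 221 |

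The three analyses at 265 to 268 agree closely, and each exceeds the true value by 49 to 52 units, a little under a quarter of 216. The 221 comes from shrinking imputed values towards no arm difference. It does not test a departure from the assumption.

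**What a tipping point would look like.** With 40 observed per arm, the standard error is 406 × √(2/40) = 90.8 and the smallest significant difference is about 1.96 × 90.8 = 178. If the estimate equals the planned 265, the one-arm delta that removes significance is (265 − 178) / 0.20 = 435, just over 1 SD. With a hypothetical estimate of 220 it is (220 − 178) / 0.20 = 210, about 0.5 SD. This is rough, because it holds the standard error at the completers' value.

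**The case against.** The best defence is that the imputation does real work. The mixed model conditions on arm, time, baseline, age, gender and baseline psychological stress. The imputation takes in all baseline and outcome variables, so baroreflex sensitivity, catecholamines and the other scales can inform the missing values. That makes missing at random more plausible, and comparing the result with a completer t-test shows whether the answer depends on observed variables. This stands. A reader might infer that agreement between the methods is automatic or says nothing about missing data. The documents do not support that: the conditioning sets differ, and the simulation gave 221 against 268 when arm was left out.

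A reader might also infer that every stopper is analysed as though still practising. That goes too far. The per-protocol rule anticipates weak adherence among those assessed, and section 8 allows temporary discontinuation with return, so donors may include people who practised little. Stoppers with no post-randomization visit are not modelled at all; they leave the analysis population.

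Nor does the plan claim robustness to departures from missing at random. Its claim for the mixed model is confined to using participants with one missing visit. And although participants know their arm, section 6.2.3 has staff and therapists withhold the hypothesised effect.

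On size, the upper figures of 1.6 points and 81 units need a one-arm departure larger than the whole planned effect (8 against 5.2; 406 against 265), so they mark the edge of a range. None of this supplies an analysis in which stoppers do worse than their observed history predicts.

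**Conclusion.** The point holds in a limited form. Both missing-data methods share one untestable assumption, post-stopping outcomes are largely uncollected, and no planned analysis departs from the assumption. Agreement would be informative about observed variables and silent about worse unobserved outcomes among stoppers.

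The likely size is moderate. Loss of the whole between-arm difference by stoppers in both arms costs about 1.0 PROMIS point or 53 HF HRV units; the one-arm range lies on either side of that, and is about halved within the defined population if half of the missing participants are excluded from it. These figures rest on assumed deltas, on 20% missing, and, except in the halved case, on covering all randomized participants. A result as large as planned would withstand a one-arm departure of up to about 1 SD; a smaller one might not. The documents do not show that the results will be biased, only that the planned check could not reveal it. The change should be made, as a cheap improvement to an analysis already planned.

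**What to change.** In section 9.6:

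- State the missing-data assumption. Describe the planned imputation as an alternative analysis under missing at random, and drop the claim of corroboration.
- Run it over all randomized participants, including those with no post-randomization visit, and name treatment arm in the imputation model.
- After imputation, shift the imputed week-6 and week-12 values by delta, separately by arm, over a range fixed in advance: for example 0 to 1 SD in the unfavourable direction (higher PROMIS Anxiety, lower HF HRV).
- For each primary outcome, report the delta, or pair of arm-specific deltas, at which the conclusion changes.

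The cost is a few lines of code on the existing imputation and one extra table. The downside is that the conclusion may look less firm.

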**Secondary hypotheses:**

1. *We hypothesize that participants with exhale>inhale versus exhale=inhale will have further decreases in stress as measured by Anxiety Sensitivity Index-3 (ASI-3), Beck Anxiety Inventory, Body Vigilance Scale, Panic Disorder Severity Scale, and Perceived Stress Scale-10 (PSS) and decreases in negative affect as measured by PROMIS Depression scale and Positive and Negative Affect Schedule-X (PANAS-X).*
2. *We hypothesize that baseline psychological stress will modify response to breathing interventions. Specifically, we hypothesize that participants with higher stress at baseline will have the further decreases in stress as measured by the PROMIS Anxiety scale.*

**Exploratory research questions:** *We consider arousal as an exploratory measure in this proposal. In our pilot, exhale>inhale versus exhale=inhale had improvements in daytime arousal as measured by the Epworth Sleepiness Scale. For the present proposal, we will examine differences in arousal from baseline, 6, to 12 weeks as measured by the Epworth Sleepiness Scale. We will also explore the relationship between baseline sleep disturbance as measured by PROMIS Sleep Disturbance and changes in arousal.*

**Specific Aim 3:** Compute the correlation between physiological and psychological changes (e.g. changes in heart rate variability correlated with changes in PROMIS Anxiety).

**Primary hypotheses:** *We hypothesize that changes in physiological and psychological measures will be moderately correlated.*

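### The Aim 3 regression and all-participant correlation do not adjust for randomised arm, so arm effects on both outcomes would modestly bias the pooled association

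*Combined protocol and SAP*

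**What the plan says.** Aim 3 concerns the association between physiological and psychological change. Section 1 (Specific Aim 3), repeated in Section 9.1, puts it this way: "We hypothesize that changes in physiological and psychological measures will be moderately correlated". No numeric threshold is given for a moderate correlation.

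Section 9.6 describes two analyses:

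- A Pearson correlation between HF HRV change and PROMIS Anxiety change at each post-randomisation assessment, "for each intervention group or for all the participants respectively, along with 95% confidence interval". The text does not say whether the per-arm or the all-participant value is the Aim 3 result.
- A supplementary model: "linear regression analysis of HF HRV changes on PROMIS Anxiety changes, age and gender will be conducted". Its terms are anxiety change, age and gender. Arm is not among them.

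The same section does include intervention as a fixed effect in the mixed models for the individual outcomes, but that term is not carried into the Aim 3 regression.

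Section 9.2 states the Aim 3 precision on the combined sample: "With a total N of 76, the study is able to detect a correlation coefficient of 0.7". The margin it attaches to that value is 0.14. Using the combined sample points towards the pooled estimate as the one the authors had in mind.

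**The concern.** The trial expects exhale>inhale to raise HF HRV more and to lower PROMIS Anxiety more (Section 9.1, Anticipated Results). If both happen, arm is a common cause of the two changes. Pooling the arms then adds a negative component, due only to the separation of the arm means, to whatever association exists among participants given the same breathing pattern.

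Randomisation does not remove this, because the regressor, anxiety change, is itself a post-randomisation outcome. Age and gender cannot stand in for arm, since under 1:1 allocation both are independent of it in expectation.

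What is at stake is the reading of Aim 3. Success on Aims 1 and 2 would by itself push the pooled correlation and the regression slope away from zero. Without an arm term, a reader cannot separate that shift from a link between the two kinds of change inside an arm.

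**Working it through.** **The plan's own figure.** The Fisher z interval for r = 0.7 at N = 76 is tanh(atanh(0.7) ± 1.96/√73) = 0.563 to 0.799. The lower half-width, 0.137, rounds to the stated 0.14 (the upper is 0.099). The figure reproduces on the pooled N.

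**Inputs (Section 9.2).**

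- HF HRV: "the difference in HF HRV between the two groups will be 265" and "The pooled SD from the two groups is 406", so d1 = 265/406 = 0.653.
- PROMIS Anxiety: 5.2 points with SD 8, so d2 = 5.2/8 = 0.65 in the opposite direction. The plan gives 5.2 as a detectable difference; treating it as the true effect is an assumption.
- 38 analysed per arm (N = 76), or 50 per arm (N = 100) with no dropout. Allocation is 1:1.
- Also assumed: normal outcomes and equal SDs in the two arms.

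**Formula.** With 1:1 allocation and within-arm SDs scaled to 1, arm separation adds d²/4 to each variance and d1·d2/4 to the covariance. Hence

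r_pooled = (r_within + d1·d2/4) / √[(1 + d1²/4)(1 + d2²/4)], with d2 negative.

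**At the planning effects with r_within = 0.** d1·d2/4 = -0.653 × 0.65/4 = -0.106. The denominator is √(1.1065 × 1.1056) = 1.106. So r_pooled = -0.096.

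**Rejection of r = 0 at 5%, two-sided (Fisher z).** The mean shift is atanh(0.096) × √73 = 0.82. The rejection probability is Φ(-1.96 + 0.82) + Φ(-1.96 - 0.82) = 0.130. At N = 100 it is 0.157.

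| HF HRV effect | Anxiety effect | Within-arm r | Pooled r | Rejects, N = 76 | Rejects, N = 100 |
|---|---|---|---|---|---|
| 265/406 | 5.2/8 | 0 | -0.096 | 13.0% | 15.7% |
| 115/406 (pilot, 173 - 58) | 5.2/8 | 0 | -0.043 | 6.6% | 7.1% |
| 300/406 | 5.2/8 | 0 | -0.107 | 15.1% | 18.5% |
| 1 SD | 1 SD | 0 | -0.20 | 41.0% | 51.5% |
| 265/406 | 5.2/8 | -0.30 | -0.367 | | |
| 265/406 | 5.2/8 | -0.70 | -0.729 | | |

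If either arm effect is zero, d1·d2 = 0 and so is the induced correlation.

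**Simulation (20,000 trials per sample size, planning effects, r_within = 0).** The pooled analysis rejects in 13.2% of trials at N = 76 and 16.0% at N = 100. The unadjusted regression slope averages about -4.9 to -5.0 HF HRV units per PROMIS point. After removing arm means, which is equivalent to adding an arm term, the mean r and the slope are about 0 and rejection is 4.8% and 4.9%. A single-arm correlation rejects in 5.0% and 4.9%. Age and gender were not simulated.

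**What effect size would be needed.** For equal effects d on both outcomes and r_within = 0, |r| = (d²/4)/(1 + d²/4), so d = 2√[r/(1 - r)]. Reaching |r| = 0.3 needs d = 1.31, and |r| = 0.5 needs d = 2.0.

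**Precision of the per-arm correlations.** With 38 in an arm, the 95% interval around r = 0 is ±tanh(1.96/√35) = ±0.32. Power against r = -0.30 is Φ(0.310 × √35 - 1.96) = Φ(-0.13) = 45%. For the arm-adjusted correlation on all 76 it is Φ(0.310 × √72 - 1.96) = Φ(0.67) = 75%.

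**The case against.** **The plan already contains an unaffected analysis.** The per-arm correlations come from the same sentence as the pooled one, and they carry no arm-mean component. At 38 per arm they are informative for strong links: the 95% interval is 0.49 to 0.83 for r = 0.7 and 0.21 to 0.71 for r = 0.5. This stands. They are weaker for smaller links (-0.02 to 0.57 for r = 0.3), they cannot reliably expose an induced r of -0.10, and they leave the regression as it is.

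**The size is modest.** A reader might infer that success on Aims 1 and 2 would be enough to confirm Aim 3. The documents do not support that. The hypothesis is a moderate correlation, and the planning value is 0.7. With an induced r of -0.096 and N = 76, the chance of an observed r beyond -0.3 is Φ[(0.096 - 0.310) × √73] = Φ(-1.82), about 3%. A true within-arm r of -0.70 would move only to -0.73, well inside the stated margin of 0.14.

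**The marginal correlation is a legitimate quantity.** Aim 3 asks only for the correlation between changes and names no null conditional on arm. Rejecting zero for the pooled correlation would be correct as a statement about the mixed population. This stands in part: the 13% is an error rate only if the result is read as evidence of association inside the arms. Adjusting does change the question answered, which is a reason to keep the unadjusted value alongside.

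**An arm term does not deliver a within-person link.** A reader might take the issue to be a missing within-person association. A correlation of change scores across participants is not one, with or without arm in the model. Adjustment yields a within-arm association and nothing more.

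**Conclusion.** The point holds in a limited form. The Aim 3 regression and the all-participant correlation omit arm, and under the trial's own hypotheses both would mix between-arm and within-arm association. At the planning effects the distortion is about -0.10 when there is no within-arm correlation, and about -0.07 when the within-arm r is -0.30 (which becomes -0.37). Read as a test of no within-arm association, a nominal 5% test would reject about 13% of the time at N = 76.

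These figures rest on real effects in both outcomes, on the 5.2-point detectable difference being true, and on normal outcomes with equal SDs. With the pilot's HF HRV difference of 115 the distortion shrinks to about -0.04.

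This is a minor-to-moderate issue for a non-primary aim. The primary outcomes and the sample size are unaffected. It still merits a change, because the plan does not say which correlation answers Aim 3, states no threshold for a moderate correlation, and sizes its precision on the pooled sample. In that setting a shift of 0.07 to 0.10 could alter how a weak-to-moderate result is described.

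**What to change.** In Section 9.6:

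1. Add randomised arm as a covariate in the Aim 3 linear regression, alongside age and gender.
2. Report an arm-adjusted (partial) correlation over all participants at each post-randomisation assessment, with its 95% confidence interval, and name it as the Aim 3 estimate.
3. Keep the per-arm correlations and the unadjusted all-participant correlation as supportive results, so that the marginal association remains visible.
4. Describe the adjusted estimate as an association among participants within arms, not as a within-person link.

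The cost is one degree of freedom and a few lines of text. No new data are needed. The one substantive consequence is that the named estimate no longer includes the joint shift produced by the intervention, and item 3 retains that information.
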